8.6.2 Serum collection

Serum collection will follow the same processing procedures as 5.2.4.4. When participants in clinic are having blood drawn as part of standard care, research tubes will be given to the phlebotomist to be drawn in addition to clinical labs.

8.6.3 Pulmonary function testing

Manual of Operating Procedures

Pulmonary function testing will be done according to the same procedure as 5.2.4.5. Data will be recorded in CRF 5a – Spirometry and Exhaled NO2.

8.6.4 Exhaled Nitric Oxide

Exhaled nitric oxide will be measured according to the same procedure as 5.2.4.6. Results will be recorded in CRF 5a – Spirometry and Exhaled NO2.

8.7 Pain Diary Processing

Completed pain diaries will be reviewed for missing data and accuracy (missing dates, ID number) and then brought to the SCC storage facility for processing. Complete pain diary entries are constituted by completion of questions 3 and 4. Diary entries with missing answers to question 3 and 4 will be considered incomplete. Diaries will be stored securely with other CRF's.

8.8 Financial Incentives/additional pain diaries

Once data collection is complete, the SRC will give the participant a second packet of pain diaries to complete over the subsequent 8 weeks. The SRC will also give the patient their financial incentives based on the number of diaries properly filled out as indicated by the schedule below (table 1).

Table 1
Timeline of financial incentives

	Visit 1 – Baseline Week 0	Visit 2 Week 8	Visit 3- end Week Obs	Observation† Week 20
Participants expected	56	50	45	45
Gift Card (\$30) -	X	X	X	X
Metro card (\$11) – travel costs	X	X	X	X
Gift card for completion of pain diaries	< 15 diaries – 0\$ 15-25 – 10\$ (50%) 26-50 – 20\$ (40%) 51-56 – 30\$ (10%)	< 15 diaries – 0\$ 15-25 – 30\$ (50%) 26-50 – 60\$ (40%) 51-56 – 90\$ (10%)	< 15 diaries – 0\$ 15-25 – 10\$ (50%) 26-50 – 20\$ (40%) 51-56 – 30\$ (10%)	< 15 diaries – 0\$ 15-25 – 10\$ (50%) 26-50 – 20\$ (40%) 51-56 – 30\$ (10%)

†Observational follow up period will continue for 4 weeks after study completion to measure adverse events, changes in pain and the proportion who choose to continue ICS.

8.9 Discharge and follow up arrangements

After completion of data collection, a follow up visit will be scheduled for 8 weeks from the current date (16 weeks after study initiation). At this point the participant will be released and any other medical care will resume.

9.1 Telephone follow up (week 12)

9.2 Overview

A follow up telephone call will be conducted 12 weeks after the patient is enrolled in the study. The goal of this phone call is to identify adverse events, to assess medication adherence, and pregnancy surveillance in female patients. Patients who become pregnant during the study will be asked to stop taking the medication and they will be withdrawn from the study. The phone script and event questionnaire (to assess for adverse events) is contained in CRF 2 – Adverse Events.

10.0 End of study visit (week 16)

10.1 Overview

The participant will return for a second in-person visit 16 weeks after study initiation. During this visit, medication administration for the purposes of research will be stopped. If the patient believes that the medication is helping them, then the medication may be continued if the patient's primary doctor agrees to this course of care. The primary doctor will be responsible for writing prescriptions for inhaled steroids or for arranging subspecialty follow up with a pulmonologist.

10.2 Intake

The participant will be greeted by the SRC when they arrive at the clinic. Prior to phlebotomy the participant will be taken to a private area for data collection.

10.3 Collection of study medication

RC2 will collect the participants study medication once they are brought to a private area. CRF 9 – 16 Adherence Status will be filled out by RC2 to document medication adherence. If at any time the participant falls below the cut-off for medication or diaries, they will be re-instructed to bring them back to compliance.

10.4 Procedures for individuals who wish to continue study medication

If a participant expresses a desire to continue the study medication long term, the first step will be to determine whether the participant received placebo or drug. RC2 will reveal which treatment arm the participant was in. Patients who received placebo will be informed that they were not given medication and that there is no indication to initiate inhaled steroids at this point. For patients who received mometasone, the PI will contact the participant's treating physician to discuss the case. Initiating long term inhaled corticosteroids will be at the treating physician's discretion.

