2.2.1 IMPROVE trial organizational chart

3.0 Study overview

We will conduct a randomized, double blind, placebo-controlled, feasibility study of mometasone furoate, an inhaled cortico-steroid (ICS), for 16 weeks in individuals with SCD and recurrent cough or wheezing who do not meet clinical criteria (derived specifically for individuals with SCD) for a diagnosis of asthma. Participants will be enrolled when they are pain free and have no acute respiratory symptoms. The sample size will be 45 participants, aged ≥ 15 , with 2:1 allocation of drug to placebo. Feasibility will be determined by the proportion of individuals successfully randomized who maintain good adherence and complete at least 30 pain diaries vs. the total number enrolled.

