4.3 Study medication

As already approved by the ISMMS research pharmacy, study medication will be stored in [name] office in a locked cabinet. Thermostat will be set at all times to maintain acceptable storage temperature (59-86 °F). Throughout the week, temperature and humidity (current readings as well as min and max for both) will be logged daily on the study medication temperature log sheet (CRF13) using a Fisher Scientific digital Traceable Thermometer/Clock/Humidity monitor. Over the weekend, min and max temperature and humidity will be logged on the Monday following. Min and max temperatures are stored after the memory is cleared (once each day). [name] packages, dispenses, and maintains accountability for all study medication is assisted by the unblinded RC in packaging and distribution.

Study packets for randomization will be made from sealable envelopes. Each packet will contain sufficient medication for 8 weeks (one 60-dose mometasone twisthaler or one placebo metered dose inhaler MDI). Packets containing active medication will include 'protocol orientation module A' (a document that has training and usage instructions for the mometasone twisthaler). Packets containing placebo will contain 'protocol orientation module B' (a document that has training and usage instructions for the placebo inhaler). Each packet will also include 60 pain diaries. Packets will then be sealed and labeled with a code. The code will indicate which treatment arm the packet corresponds to. The unblinded RC will have access to a master list that reveals the coding scheme, SRC and PI will not have access to this list.

In the event that [name] is not present during study recruitment/enrollment, licensed nurse practitioner [name] will be present to oversee dispensation of study drug or placebo.

5.1 Recruitment, screening and eligibility procedures:

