5.3.4 Randomization and Enrollment

5.3.4.1 Overview

Individuals who meet inclusion/exclusion criteria will then be consented and randomized. The enrollment procedure is designed to maintain blinding of the participant, the PI and the senior RC. One RC will be unblinded (RC2) for purposes of introducing the study medication, training in proper use of the medication and refilling medication if the participant loses their medication.

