10.5 Data collection

The 16-week questionnaire will include data regarding respiratory symptoms, medication adherence, health-related quality of life, adverse events, side effects, and pregnancy surveillance in female patients. Patients who become pregnant during the study will be asked to stop taking the medication and they will be withdrawn from the study. Once it is confirmed by RC2 that the participant will remain in the study, CRF 6 – End of Study Questionnaire will be administered by the SRC.

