11.4 Data collection

The 20-week questionnaire will include data regarding respiratory symptoms, pain and stiffness modules of health-related quality of life, adverse events, and pregnancy surveillance in female patients. Patients who become pregnant during the study will be asked to stop taking the medication and they will be withdrawn from the study. The questionnaire will also ask for updated contact information for the participant. CRF 7 – Post Protocol Questionnaire will be administered by the SRC or RC2.

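### For participants who ask to continue, nothing in 10.4 or 11.3 stops the arm being revealed before that visit's self-reported data are collected

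*Combined protocol and SAP*

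**What the plan says.** Section 3.0 sets the design: "We will conduct a randomized, double blind, placebo-controlled, feasibility study of mometasone furoate". Section 5.3.4.1 says that "The enrollment procedure is designed to maintain blinding of the participant, the PI and the senior RC", and section 4.3 says of the arm-code list that "SRC and PI will not have access to this list". Only the second coordinator (RC2) is unblinded.

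At week 16, RC2 takes back the inhaler (10.3). Section 10.4 then covers participants who want to go on with the medication: "RC2 will reveal which treatment arm the participant was in". Those on placebo are told so. For the others, "For patients who received mometasone, the PI will contact" the treating physician. Section 10.5 follows with the questionnaire on symptoms, adherence, quality of life, adverse events and side effects. The SRC gives it: "Once it is confirmed by RC2 that the participant will remain in the study, CRF 6" is administered. Section 10.7 hands out diaries for four more weeks.

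Sections 11.3 and 11.4 have the same order at week 20. The questionnaire there (CRF 7) covers respiratory symptoms, "pain and stiffness modules of health-related quality of life, adverse events" and pregnancy surveillance, and may be given by the SRC or by RC2.

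**The concern.** A blinded trial normally completes a participant's assessments before the code is broken for that participant. Here the manual provides for a code break at the end-of-treatment visit, lists it ahead of the self-report, and sets no rule on which comes first. The people affected are not a random subset: section 10.1 offers continuation to patients who believe the medication is helping.

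At stake are the outcomes that section 14.3 collects as candidates for a definitive trial: quality of life (ASCQ-Me change), respiratory symptoms, safety and diary pain. An answer given after the arm is known may reflect that knowledge as well as the drug. Sections 14.5 to 14.7 have no step that identifies or separates such data. The PI, meant to be blinded, also learns the arm of some participants while still holding responsibilities for data and safety review.

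**Working it through.** No figure in the plan is in dispute, so the check sets the sections side by side.

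**1. Order within the week-16 visit, as written**

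| Section | Step | Who |
|---|---|---|
| 10.3 | Inhaler returned, adherence form | RC2 |
| 10.4 | Arm revealed, if the participant asks to continue | RC2, then PI for mometasone |
| 10.5 | CRF 6 | SRC, after RC2's confirmation |
| 10.6 | Completed diaries reviewed | not stated |
| 10.7 | Diaries issued for weeks 16–20 | SRC |

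Section 10.5 makes CRF 6 wait for RC2's confirmation, so RC2 is involved before the questionnaire. Section 10.4 makes finding out the arm the first step once the wish is voiced. A participant who voices it while handing back the inhaler would, under the manual as written, be told before CRF 6. No sentence prevents this, and none states that it must happen.

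**2. Data by position relative to a reveal**

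- *Before any reveal:* eNO and sVCAM change at week 8 (14.4), all week-8 self-report (8.6.1), and diary entries made before week 16.
- *Possibly after:* CRF 6 at week 16. For a first reveal at week 20, CRF 7.
- *Necessarily after a week-16 reveal:* the week 16–20 diaries (10.7) and CRF 7 (11.4), whatever the order within the week-16 visit.
- *Little affected:* feasibility, which rests on follow-up, diary counts and dose counters (14.2).

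Section 14.3 does not say which visit the ASCQ-Me change uses, and section 14.7 sets no time window for the diary model. Post-reveal data are therefore not excluded from either.

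**3. The PI**

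The PI contacts physicians of requesters who had mometasone (10.4, 11.3), so each contact discloses an arm. The PI also signs off every CRF before it is final (2.3) and reviews adverse-event reports weekly (15.2). Nothing requires sign-off to come before the contact.

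**4. How many, and how much**

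Section 3.0 gives 45 participants at 2:1: 45 × 2/3 = 30 on mometasone and 45 × 1/3 = 15 on placebo. Those are ceilings on the number who could ask. The documents give no expected share.

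Suppose, purely as an assumption, that the same share *f* of each arm is revealed before CRF 6, and that knowing the arm shifts the mean answer by *b* in opposite directions. The spurious difference is *fb* − (−*fb*) = 2*fb*: 0.2*b* at *f* = 0.10, 0.5*b* at *f* = 0.25, 1.0*b* at *f* = 0.50, and zero if CRF 6 always comes first. Neither *f* nor *b* is in the documents. Equal shares and opposite shifts are assumptions too.

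**The case against.** **The order is inferred.** This stands in part. Section 10.4 is a contingency with no time point, and the manual's numbering is not strict chronology: the week-8 refill (8.4) depends on criteria to remain in the study, yet the adherence check comes next (8.5), and 5.3.3 ends in randomization before consent is described in 5.3.4.2. The confirmation by RC2 also appears at week 8, where no reveal exists, so it does not by itself date the reveal. A reader might infer that the plan orders CRF 6 to follow the reveal, or that every participant is unblinded at week 16. The documents support neither. The order is permitted, and it affects only those who ask. The week 16–20 exposure does not depend on this.

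**The PI's unblinding is limited.** This stands. A reader might infer that the PI learns the arm of placebo requesters by not being asked to call. That needs the PI to know of the request, which no section states. Section 16.0 also has the PI offer to contact providers of placebo patients, apparently after analysis. The SRC, who gives CRF 6, is not said to be told the arm.

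**Size and direction.** A reader might set a bias in points against the 1-point difference in 14.8. That figure concerns mean pain scores from diaries, and entries made before week 16 cannot be changed by a later reveal; no 1-point target exists for anything in CRF 6. Nor is a bias towards mometasone established: knowing one took a steroid could raise side-effect reports.

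**Blinding was weak already.** The inhalers differ by arm (4.3) and the active-arm leaflet names the product. But both orientation modules tell participants that their inhaler may hold placebo or mometasone, so being told the arm is still new information.

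**Little hangs on it.** The primary outcome is feasibility, clinical effects are expected to be imprecise, and weeks 16–20 serve partly to count who continues inhaled steroids. This limits the importance. Table 1's footnote, however, also assigns that period to adverse events and changes in pain, which are open to knowledge of the arm.

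**Conclusion.** The point holds as a gap in the protection of blinding, confined to participants who ask to continue. For them, week-16 quality of life, respiratory symptoms, side effects and self-reported adherence can be collected unblinded; for anyone revealed at week 16, the week 16–20 diaries and CRF 7 necessarily are. The PI learns which requesters had mometasone, possibly before signing off their forms. The main feasibility result, the week-8 biomarkers and diaries completed before week 16 are essentially untouched.

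The size and direction of any bias cannot be derived: the number of requesters (at most 45), their split by arm and the effect of knowing the arm are all unstated. The conclusion rests only on the written procedures and on the absence of a rule completing the data first. It should be corrected because the exposed measures are candidate outcomes for the next trial and the correction is cheap.

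**What to change.** - In 10.4 and 11.3, state that the arm may be revealed only after that visit's questionnaire (CRF 6 or CRF 7), adverse-event questions and diary collection are complete. Move both sections after data collection and diary processing.
- Have the PI contact the treating physician only after signing off that participant's CRFs for the visit.
- Log each reveal with its date, and flag post-reveal week 16–20 data as unblinded in the analysis.

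The cost is a few minutes' wait for the participant, a short delay before the physician is contacted, and one extra log. Week 16–20 data from participants revealed at week 16 remain unblinded under this change; the flag makes that visible but does not remove it.

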10.5 Data collection

The 16-week questionnaire will include data regarding respiratory symptoms, medication adherence, health-related quality of life, adverse events, side effects, and pregnancy surveillance in female patients. Patients who become pregnant during the study will be asked to stop taking the medication and they will be withdrawn from the study. Once it is confirmed by RC2 that the participant will remain in the study, CRF 6 – End of Study Questionnaire will be administered by the SRC.

10.6 Pain Diary Processing

Manual of Operating Procedures

Completed pain diaries will be reviewed for missing data and accuracy (missing dates, ID number) and then brought to the SCC storage facility for processing. Diaries will be stored securely with other CRF's.

10.7 Financial Incentives/additional pain diaries

Once data collection is complete, the SRC will give the participant a new packet of pain diaries to complete over the subsequent 4 weeks. The SRC will also give the patient their financial incentives based on the number of diaries properly filled out as indicated by table 1.

10.8 Discharge and follow up arrangements

After completion of data collection, a follow up visit will be scheduled for 4 weeks from the current date (20 weeks after study initiation). At this point the participant will be released and any other medical care will resume.

11.0 Post-protocol observation period visit (week 20)

11.1 Overview

The participant will return for a final, post-protocol visit 4 weeks after completion of the study. The goal of this visit will be to assess for adverse events in individuals who discontinued inhaled corticosteroids. Participants who noted substantial worsening of symptoms (SCD or breathing related) will be given the opportunity to have research staff speak with their primary treating physician regarding initiation of long term use of inhaled steroids. The primary doctor will be responsible for writing prescriptions for inhaled steroids or for arranging subspecialty follow up with a pulmonologist.

11.2 Intake

The participant will be greeted by the SRC when they arrive at the clinic. Prior to phlebotomy the participant will be taken to a private area for data collection.

11.3 Procedures for individuals who wish to continue study medication

If a participant expresses a desire to continue the study medication long term, the first step will be to determine whether the participant received placebo or drug. RC2 will reveal which treatment arm the participant was in. Patients who received placebo will be informed that they were not given medication and that there is no indication to initiate inhaled steroids at this point. For patients who received mometasone, the PI will contact the participant's treating physician to discuss the case. Initiating long term inhaled corticosteroids will be at the treating physician's discretion.

11.4 Data collection

The 20-week questionnaire will include data regarding respiratory symptoms, pain and stiffness modules of health-related quality of life, adverse events, and pregnancy surveillance in female patients. Patients who become pregnant during the study will be asked to stop taking the medication and they will be withdrawn from the study. The questionnaire will also ask for updated contact information for the participant. CRF 7 – Post Protocol Questionnaire will be administered by the SRC or RC2.

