5.3.4.3 Baseline data collection

After the participant has completed the informed consent process, CRF 3 will be completed again to ensure the patient's eligibility to be a part of the study. Then the senior RC will administer CRF 4 the baseline data collection form.

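### Section 11.4 lets the unblinded coordinator administer the week-20 questionnaire, although the blinded coordinator administers it at every earlier in-person visit

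*Combined protocol and SAP*

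**What the plan says.** Section 3.0 describes the trial as double blind. Under 5.3.4.1 the enrollment procedure is "designed to maintain blinding of the participant, the PI and the senior RC", and the same paragraph sets one exception: "One RC will be unblinded (RC2) for purposes of introducing the study medication", along with inhaler training and replacement of lost medication. Section 4.3 says of the master code list that "SRC and PI will not have access to this list".

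The interviewer is named visit by visit. At baseline (5.3.4.3): "Then the senior RC will administer CRF 4 the baseline data collection form". At week 8 (8.6.1) CRF 5 is given by the SRC. At week 16 (10.5) the sentence begins "Once it is confirmed by RC2 that the participant will remain in the study, CRF 6" and again names the SRC as the person who administers the form. At week 20 (11.4) CRF 7 "will be administered by the SRC or RC2".

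The same section gives the content of the week-20 questionnaire: "respiratory symptoms, pain and stiffness modules of health-related quality of life, adverse events, and pregnancy surveillance in female patients".

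**The concern.** CRF 7 asks participants to report symptoms, pain and adverse events to an interviewer. RC2 knows which participants have just stopped an active steroid and which have stopped placebo, and could, without intending to, probe for worsening or code answers differently by arm.

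The visit has a specific purpose. Section 11.1 gives its goal as assessing adverse events in people who have come off inhaled corticosteroids, and the footnote to Table 1 adds changes in pain and the proportion who go on with treatment. It is the only in-person visit after research medication ends at week 16, so no later visit could correct a biased interview. Participants who report substantial worsening are also offered contact between staff and their treating physician, so the answers have a use beyond description.

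**Working it through.** No arithmetic applies. The check compares the named interviewer at each in-person visit with that person's stated blinding status.

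| Visit | Questionnaire | Named interviewer | Status | Section |
|---|---|---|---|---|
| Baseline | CRF 4 | SRC | blinded | 5.3.4.3 |
| Week 8 | CRF 5 | SRC | blinded | 8.6.1 |
| Week 16 | CRF 6 | SRC | blinded | 10.5 |
| Week 20 | CRF 7 | SRC or RC2 | RC2 unblinded | 11.4 |

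**Does RC2 need to give CRF 7?** RC2's own forms at weeks 8 and 16 are the adherence checks, CRF 8 (8.5) and CRF 9 (10.3). For CRF 8 the stated reason is that the inhaler has to be seen, which would unblind anyone else. Section 11.4 lists no such task for CRF 7. RC2's stated task at week 20 is the arm reveal under 11.3, which can follow the questionnaire.

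**Is the choice controlled?** The text supplied gives no rule for choosing between the SRC and RC2, and no requirement to record who conducted the interview.

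**Is the SRC at the visit?** Yes. The SRC greets the participant (11.2) and hands over the incentives after data collection (11.6).

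**Which data can be affected?**
- Feasibility (14.2) rests on completed follow-up, diary counts and dose counters. The answers given on CRF 7 do not enter it.
- The Aim 2 primary outcomes, eNO and sVCAM, are measured 8 weeks after randomization (14.4).
- Pain diaries are filled in by participants, and a new packet covers the 4 weeks after week 16 (10.7).
- Section 14 names no between-arm analysis of week-20 questionnaire data. Sections 14.3 and 14.7 list quality of life, respiratory symptoms and safety as exploratory measures without tying them to week 20.

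What remains exposed is the interviewer-collected, exploratory content of CRF 7.

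**The case against.** The case for leaving 11.4 alone is that no primary outcome depends on CRF 7, that the visit is a largely descriptive post-protocol observation, and that in a 45-person trial it may be worth giving up some assessor blinding to avoid missed interviews. The SRC is named first and is already at the visit, which is consistent with RC2 being only a back-up, although the text does not say so. The blind is also already partial by then. From week 16, RC2 tells any participant who wishes to continue which arm they were in, and for those on mometasone the PI contacts the treating physician (10.4).

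Most of this stands as a limit on weight. It does not justify leaving the choice of interviewer open and unrecorded. The planned reveal covers only participants who ask to continue; for the others no unblinding is planned before week 20.

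A reader might infer more than the documents support:

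- **That the trial's main results are compromised.** They are not, for the reasons given in the working.
- **That adverse events were always collected blind before week 20.** The calls at weeks 2, 4 and 12 (6.2, 7.2, 9.2) also collect them and name no caller, so the contrast holds for in-person visits only.
- **That everything on CRF 7 is subjective.** The form itself is not in the supplied text. The serious events in 1.4.3 include death, intubation and intensive care admission, which do not depend on how a question is put.
- **That a change of interviewer confounds the post-withdrawal change.** It could disturb within-person change in CRF 7 items. It biases the comparison between arms only if the choice or conduct of the interviewer differs by arm, which the documents do not show. The self-completed diaries give a separate record of pain.
- **That all 45 participants expected at week 20 in Table 1 would be interviewed unblinded.** This is a ceiling, with nothing in the text to say how often RC2 would act.

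**Conclusion.** The inconsistency is real and of low consequence. Section 11.4 departs, without a stated reason, from the blinded-interviewer arrangement at the other three in-person visits, and so allows avoidable interviewer bias in exploratory week-20 symptom, quality-of-life and adverse-event data.

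Its size cannot be derived: the documents give neither the share of interviews that RC2 would conduct nor any measure of interviewer effect. The conclusion assumes that the SRC remains blinded as 5.3.4.1 intends and that CRF 7 is asked by an interviewer, as the wording of 11.4 implies.

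It would also be too strong to read the remedy as making week 20 a blinded assessment. Participants told their arm at week 16 carry that knowledge into the interview, whoever asks the questions. This is a worthwhile improvement and not a flaw that threatens the trial's conclusions.

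**What to change.** Change 11.4 so that the SRC administers CRF 7, and require the form to be completed before any arm is revealed under 11.3 at that visit. RC2 keeps the reveal.

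If the SRC is unavailable and RC2 has to act as back-up, record who administered CRF 7. In all cases record whether the participant had already been unblinded at week 16 under 10.4. Report week-20 comparisons as not fully blinded wherever either applies.

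The schedule of changes shows data collection ending in October 2016. For interviews already done, the part that can still be acted on is recovering these two facts where records allow and reporting accordingly; the wording change serves any later trial that reuses this manual.

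The cost is slightly less scheduling flexibility, eased by the back-up provision, and two added items of information. No clinical rule changes.
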